13.3.2. Treatment State

Within each study phase (based on assignment of study phase described in [Section 13.3.1](#)), only those events/assessments which occur within the ranges shown in Table 11 will be considered ‘on-treatment’ for the given phase. No treatment states will be assigned to medications.

For adverse events, partial AE start date will use imputation as described in 13.6.2.1.

Table 11 Treatment State within Study Phases

Study Phase	State	Definition
Screen	Pre-Treatment	All assessments/events within phase
Intervention/Extension	On-treatment	Date ≤ max (Date of Last CAB LA +RPV LA IM Dose + 63, Date of Last Dose of Oral Study Treatment (CAB+RPV or SOC Bridging) +1)
	Post-Treatment	Date > max (Date of Last CAB LA +RPV LA IM Dose + 63, Date of Last Dose of Oral Study Treatment (CAB+RPV or SOC Bridging) +1)
Long Term Follow-Up	Post-Treatment	All assessments/events within phase
NOTES: 
 • Date = Assessment/Start Date a. Treatment State is determined after data has been assigned to the study phases as defined in Section 13.3.1. b. Last injection and/or last dose of oral study treatment (CAB+RPV or SOC bridging) are only applied to participants who permanently discontinued the study treatment. The assessments for participants who did not permanently discontinue the study treatment will be considered ‘On-treatment’. For participants continuing into extension phase, all data assigned to intervention phase per Section 13.3.1 will be considered ‘On-treatment’. 		

13.3.3. Oral Lead-in Period

Certain displays will be produced for data collected or events occurring during the oral-lead-in period as defined in Table 12 and Table 13.

Table 12 Oral Lead-in Period for AEs

Study Period	Date Range
Oral Lead-in	
For participants receiving at least one Injection: Intervention Treatment Start Date ≤ Date ^[a] < Date of First IM Injection
 
For participants withdrawing prior to first Injection: Date ≥ Intervention Treatment Start Date
 
Note that the oral lead-in period is only applicable to the participants who received at least one dose of study treatment during the oral lead-in period in the study. Oral lead-in period is within the intervention phase.

[a] AEs with completely missing start date which have been assigned to the Intervention Phase based on Table 7 will not be assigned to the Oral Lead-in Period.
	

NOTES:

- Date = AE Start date

Table 13 Oral Lead-in Period for Laboratory Data

Period	Date Range
Oral Lead-in	
For participants receiving at least one Injection: Intervention Treatment Start Date < Date ≤ Date of First IM Injection
 
For participants withdrawing prior to first Injection: Date > Intervention Treatment Start Date
 
Note that the oral lead-in period is only applicable to the participants who received at least one dose of study treatment during the oral lead-in period in the study. Oral lead-in period is within the intervention phase.

NOTES:

- Date = Date of assessment

13.4. Appendix 4: Data Display Standards & Handling Conventions

13.4.1. Reporting Process

Software	

 The currently supported versions of SAS software will be used. 	
Reporting Area	
HARP Server	us1salx00259
HARP Compound	\ARPROD\GSK1265744\mid213199\interim_01 \ARPROD\GSK1265744\mid213199\interim_02 \ARPROD\GSK1265744\mid213199\primary_01
Analysis Datasets	

 Analysis datasets will be created for the interim analyses according to SI data standards. Analysis datasets will be created for the Month 12 reporting effort according to CDISC standards (SDTM IG Version 3.2 & ADaM IG Version 1.1). 	
Generation of RTF Files	

 RTF files will be generated for all reporting efforts described in the RAP. 	

13.4.2. Reporting Standards

General	

 The current GSK Statistical Display Standards in the GSK Standards Library (IDSL) will be applied for reporting, unless otherwise stated (Library Location: https://spope.gsk.com/sites/IDSLLibrary/SitePages/Home.aspx): 
 4.03 to 4.23: General Principles 5.01 to 5.08: Principles Related to Data Listings 6.01 to 6.11: Principles Related to Summary Tables 7.01 to 7.13: Principles Related to Graphics 	
Formats	

 GSK Statistical Display Principles (5.03 & 6.06.3) for decimal places (DP's) will be adopted for reporting of data based on the raw data collected, unless otherwise stated. Numeric data will be reported at the precision collected on the eCRF. The reported precision from non eCRF sources will follow the GSK Standard Statistical Display Principles but may be adjusted to a clinically interpretable number of DP's. 	
Planned and Actual Time	

 Reporting for tables, figures and formal statistical analyses: 
 Planned time relative to dosing will be used in figures, summaries, statistical analyses and calculation of any derived parameters, unless otherwise stated. The impact of any major deviation from the planned assessment times and/or scheduled visit days on the analyses and interpretation of the results will be assessed as appropriate. Reporting for Data Listings: 
 Planned and actual time relative to study drug dosing will be shown in listings (Refer to GSK Standard Statistical Display Principle 5.05.1). Unscheduled or unplanned readings will be presented within the participant's listings. 	

Unscheduled Visits	

 • Unscheduled visits will be assigned to an analysis visit using the all-inclusive windows defined in Section 13.2. • However, data summaries will only report visits that are planned assessment time points for each parameter (according to the Schedule of Activities in Section 13.1.1). • Evaluable assessments at unscheduled visits will be used when categorizing values across visits, such as 'maximum grade during the intervention phase' or 'at any time post-baseline', and for any algorithm that has specific rules for which observation to use (e.g. snapshot algorithm or CVF identification). 	
Descriptive Summary Statistics	
Continuous Data	Refer to GSK Standard Statistical Display Principle 6.06.1
Categorical Data	N, n, frequency, %
Graphical Displays	

 • Refer to GSK Standard Statistical Display Principals 7.01 to 7.13. 	

13.4.3. Reporting Standards for Pharmacokinetic Data

Pharmacokinetic Concentration Data	
Descriptive Summary Statistics, Graphical Displays and Listings	
Refer to the GSK Standard PK Display Standard.
 
Refer to the GSK Standard Statistical Display Principle 6.06.1.
 
Note: Concentration values will be imputed as per GUI_51487 for descriptive summary statistics/analysis and summarized graphical displays only.

13.5. Appendix 5: Derived and Transformed Data

13.5.1. General

Multiple Measurements at One Analysis Time Point
 
 • If there are two values within a time window (as per Section 13.2.1) the value closest to the target day for that window will be used. If values are the same distance from the target, then the mean (geometric mean for HIV-1 RNA, arithmetic mean for all other measurement) will be taken. • Assessments not chosen for use in summary statistics by this algorithm will still appear in the associated listings. • All applicable valid assessments, irrespective of proximity to the target study day, will be used when categorizing values across visits, such as ‘maximum grade during the intervention phase’ or ‘at any time post-baseline’, and for any algorithm that has specific rules for which observation to use (e.g. snapshot algorithm, LOCF or CVF identification). • Participants having both High and Low values for Normal Ranges at any post-baseline visit for safety parameters will be counted in both the High and Low categories of “Any visit post-baseline” row of related summary tables. This will also be applicable to relevant Potential Clinical Importance summary tables.

Treatment Start Date
 
 • Intervention Phase Treatment Start Date = Earliest date of CAB + RPV oral lead-in entered in the IP exposure eCRF form

Nominal Month 14 Visit Date
 
 • For participants who received Month 14 injection, the nominal Month 14 visit date is defined by the Month 14 injection date. • Otherwise, nominal Month 14 visit date is defined by the date of latest Month 14 assessment. • For participants who continued into Extension Phase but missed the Month 14 visit, the nominal Month 14 visit date is defined by the last contact date prior to the date of the first nominal extension phase visit (i.e. Month 16, Month 18, etc.).

Study Day
 
 • The Study Day of an event (e.g., lab assessment, vital sign, ECG, start date of AE or HIV associated condition) will be derived as the number of days between the date of the event and the Intervention Phase treatment start date as follows: 
 ○ If date of event \geq start date of study treatment, then 
 ▪ Study Day = Date of Event - Intervention Phase Treatment Start Date +1 ○ If date of event $<$ start date of study treatment, then 
 ▪ Study Day = Date of Event - Intervention Phase Treatment Start Date • Note that the start date of intervention phase study treatment is on Study Day 1 and the day before this is Study Day -1; i.e., there is no Study Day 0.

Long Term Follow-up Study Day

 Participants are considered to have entered LTFU if they have a post-treatment, non-bridging ART medication start date or a LTFU visit entered in the CRF. The Long-Term Follow Up (LTFU) Study Day of an event (e.g., lab assessment, start date of AE or HIV associated condition) will be derived as the number of days between the date of the event and the end of IP treatment [i.e. min(LTFU ART Start Date, max>Last IM Injection Date, Last Oral Bridging End Date)] as follows: 
 If the date of event falls in Long-term Follow up phase, then 
 LTFU Study Day = Date of event - min(LTFU ART Start Date, max>Last IM Injection Date, Last Oral Bridging End Date) + 1
Study Treatment

 Refers to CAB+RPV oral lead-in, CAB + RPV oral bridging, SOC bridging, CAB LA + RPV LA
Change from Baseline

 Post-Dose Visit Value – Baseline 
 Unless otherwise specified, the baseline definitions specified in Section 5.2 will be used for derivations for endpoints / parameters.

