13.2. Appendix 2: Assessment Windows

13.2.1. Definitions of Assessment Windows for Analyses

Laboratory data, vital signs, adverse events, and genotypic/phenotypic data will be assigned to assessment windows according to actual dates rather than the nominal visit labels as recorded on the eCRF or in the laboratory database.

Prior to visit slotting, assessments are first assigned to a study phase (Screening, Intervention Phase, Extension, or Long Term Follow Up) as defined in [Appendix 3](#).

According to the protocol, the nominal target study visit date will be based on the first injection, the Month 1 date. For instance, if Month 1 occurred on July 7th, all subsequent visits are expected to occur on the 7th of each month such that subsequent visits will be August 7th, September 7th, October 7th, etc. Since there are not >28 days in every month of the year, if the Month 1 injection occurred on the 29th, 30th, or 31st of the month, then the target study visit date for the remainder of the visits will be the 28th of the month.

The nominal target study visit day is derived as

- **M1 Target Day** = Date of Actual M1 Injection Visit Date – Date of First Oral lead-in Dose + 1, if subject receives M1 injection; else M1 Target Day = 30.
- **Mx Target Day** = Mx Nominal Target Study Visit Date – Date of First Oral lead-in Dose + 1, for x=2,3, ...

Assessment windows will be derived based on the midpoint between two consecutive planned target study visit dates. For the Snapshot efficacy data, the same approach will be used, except for Month 12, which will use a +/- 6-week window around the projected target study visit date at Month 12.

For parameters which are not scheduled to be assessed at visits, the all-inclusive assessment windows will still be used; however, data summaries will only report scheduled visits. Assessments at unscheduled visits will be included in summaries of worst-case values across visit (e.g. during the intervention phase) and in data listings, as well any algorithms that make use of additional data (e.g., Snapshot).

For participants transitioning to commercial product at EOS, the safety follow-up visit date will be the last date referenced and serve as the ending timepoint for the final visit window.

Table 1 Assessment Windows for Screening, Intervention and Extension Phase Data (Excluding HIV-1 RNA)

Target (Study Day)	Analysis Window		Analysis Timepoint
	Beginning Timepoint	Ending Timepoint	

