Extension Phase	
For subjects transitioning to commercial product: Date of Nominal Month 14 Injection ≤ Date ≤ Safety Follow-up visit date
 
For subjects not transitioning to commercial product: Date of Nominal Month 14 Injection ≤ Date < LTFU ART Start Date ^[a]
 
For AEs leading to treatment withdrawal with start date equal to the LTFU ART Start Date, Extension Phase instead of Long-Term Follow-up Phase will be assigned.

Long Term Follow-Up	
For subjects who receive at least one CAB/RPV injection and permanently discontinue study treatment: AE Start Date ≥ LTFU ART Start Date

AEs with completely missing start date:
 
 • If AE end date is ≤ Intervention Phase Treatment Start Date, then assign to Screening Phase; • Else if AE end date is completely missing or Intervention Phase Treatment Start Date < AE end date ≤ Date of Nominal Month 14 Injection, then assign to Intervention Phase; • Else if AE end date > Date of Nominal Month 14 Injection, then assign to Extension Phase. 	

- Date=AE Start Date
- [a] If participants have missing LTFU ART start date, only the lower bound will be considered in the derivation.

Table 8 Study Phases for Laboratory, Vital Signs, HIV-1 Associated Conditions, and Protocol Deviation Data

Study Phase	Definition
Screen	Date ≤ Study Treatment Start Date
Intervention Phase	
For subjects continuing into the Extension Phase: Intervention Phase Treatment Start Date < Date < Date of Nominal Month 14 Visit
 
For subjects not continuing into the Extension Phase: Intervention Phase Treatment Start Date < Date ≤ LTFU ART Start Date ^[a]
 
For subjects transitioning to commercial product without discontinuing or entering Extension: Intervention Phase Treatment Start Date < Date ≤ Safety Follow-up visit date

Extension Phase	
For subjects continuing into Extension Phase: Date of Nominal Month 14 Visit ≤ Date ≤ LTFU ART Start Date ^[a] or Safety Follow-up visit date

Long Term Follow-Up	
For subjects who receive at least one CAB/RPV injection and permanently discontinue study treatment: Assessment Date > LTFU ART Start Date

- Date = start or assessment date
- [a] If participants have missing LTFU ART start date, only the lower bound will be considered in the derivation.

Study phase of discontinuation will be determined according to Table 9.

Table 9 Study Phases for Study Conclusion/IP Discontinuation

Study Phase	Definition

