13.5.3. Efficacy

Efficacy
Snapshot

 The Snapshot algorithm is intended to be primarily a virologic assessment of the endpoint, and as such follows a “virology first” hierarchy. ‘HIV-1 RNA < 50 c/mL’ or ‘HIV-1 RNA ≥ 50 c/mL’ within an analysis window (see Table 2 and Table 3) is typically determined by the last available HIV-1 RNA measurement in that window while the participant is On-treatment in the Intervention Phase (as assigned based on Section 13.3). When no HIV-1 RNA data is available within a window, a participant cannot be assigned to the category of ‘HIV-1 RNA < 50 c/mL’. Depending on the reason for lack of data, the participant will be classified as ‘HIV-1 RNA ≥ 50 c/mL’ or reported as ‘No Virologic Data at Week X’; in the latter case, the algorithm further classifies the nature of the missing data. Typically, a participant withdrawn (i) due to AE or, (ii) for another reason yet was suppressed at the time, will be counted as ‘No Virologic Data at Week X’. Should a participant withdraw for reasons other than AE and was not suppressed at the time, they will be categorized as ‘HIV-1 RNA ≥ 50 c/mL’. Full details of the algorithm, including the handling of special cases, are included in Appendix 8: Snapshot Algorithm Details.
Plasma HIV-1 RNA

 HIV-1 RNA results may be provided as censored values, such as <40 or >9,999,999 c/mL. For the purposes of summary statistics, such values will be replaced by the next value beyond the limit of detection, e.g., 39 or 10,000,000 c/mL, respectively, for the given examples. Data listings will show the censored values as provided.
Confirmed Virologic Failure (CVF)

 For the purposes of clinical management in this study, CVF is defined as: 
 Rebound as indicated by two consecutive plasma HIV-1 RNA levels ≥ 200 c/mL. The CVF definition is provided in the protocol Section 7.1.7 Only plasma HIV-1 RNA values determined by the central laboratory will be used to assess virologic failure.
CDC Classification for HIV-1 Infection (2014)

 CDC HIV-1 Classification at Baseline is collected in eCRF and no derivation will be performed programmatically for analysis purposes. Please refer to study protocol for detail description of CDC HIV-1 Classification.

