13.8. Appendix 8: Snapshot Algorithm Details

Detailed Algorithm Steps

 • Consider an analysis visit window for Month X as defined in Table 2. • The HIV-1 RNA threshold of 50 will be analysed in this study • The COVID-19 pandemic presents significant logistical challenges for many clinical sites around the world, with variable restrictions being placed on site resources and operations, and on an individual participants ability to attend clinic visits. The snapshot algorithm is modified to allow for the presentation of full scope of COVID-19 relatedness. The analysis window for 'Month 12' and HIV-1 RNA threshold of '50 c/mL' are used for the purpose of illustration. A participant's Snapshot response and reason at Month 12 are categorized as below. 
 ○ HIV-1 RNA < 50 c/mL ○ HIV-1 RNA ≥ 50 c/mL 
 Data in window not below 50 
 Non-COVID-19 related 
 Discontinued for lack of efficacy Discontinued for other reason while not below 50 COVID-19 related 
 Discontinued for lack of efficacy Discontinued for other reason while not below 50 ○ No Virologic Data at Month 12 Window 
 Non-COVID-19 related 
 Discontinued study due to AE or death Discontinued study for other reasons On study but missing data in window COVID-19 related 
 Discontinued study due to AE or death Discontinued study for other reasons On study but missing data in window Change in background therapy* 
* Note: Use of CAB + RPV oral bridging and SOC oral bridging medication, where the latter is due to unavailability of CAB/RPV IM injections or oral CAB+RPV during the pandemic, will not be considered a "Change in background therapy" in the Snapshot algorithm. All other permanent changes in ART are not permitted in this protocol.

Detailed steps
 
 • Please note that the following scenarios will NOT be penalized in the Snapshot algorithm Oral bridging (CAB+RPV or SOC, where SOC oral bridging medication is permitted during COVID-19 pandemic due to the unavailability of the CAB/RPV IM injections and oral CAB+RPV)

Detailed Algorithm Steps		
Condition ('Month 12' indicates Month 12 window)	Response	Reasons

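### The fallback date for a missed Month 14 visit can fall on the Month 12 sample or its retest and move that viral load out of the Month 12 Snapshot

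*SAP*

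**What the plan says.** SAP 13.5.1 defines the nominal Month 14 visit date in three steps. It is the Month 14 injection date if that injection was given, and otherwise the date of the latest Month 14 assessment. For participants who went on into the Extension Phase but missed Month 14, "the nominal Month 14 visit date is defined by the last contact date prior to the date of the first nominal extension phase visit".

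That date separates the two phases. For laboratory data of continuing participants, Table 8 in SAP 13.3.1 defines the Intervention Phase as "Intervention Phase Treatment Start Date < Date < Date of Nominal Month 14 Visit" and starts the Extension Phase with "Date of Nominal Month 14 Visit ≤ Date ≤ LTFU ART Start Date". A sample dated exactly on the boundary is therefore Extension data.

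SAP 13.2.1 fixes the order of derivation: "Prior to visit slotting, assessments are first assigned to a study phase". SAP 13.5.3 says the Snapshot outcome is typically decided by the "last available HIV-1 RNA measurement in that window while the participant is On-treatment in the Intervention Phase". Appendix 8 begins: "Consider an analysis visit window for Month X as defined in Table 2". Table 2 covers Screening and Intervention Phase HIV-1 RNA and gives Month 12 a window of target day ±42 days.

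Protocol 7.1.8.1 asks participants with 50 c/mL or more at Month 12 to return for a repeat within 4 weeks, so that the repeat falls in the same analysis window.

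**The concern.** The fallback has no lower bound. The last contact before the first Extension visit can be the Month 12 visit itself, or the Month 12 retest. The strict inequality in Table 8 then moves that day's viral load into the Extension Phase before any window is applied. A participant with a measured, suppressed Month 12 result would be reported as on study with data missing. A participant whose retest was suppressed would be reported at 50 c/mL or more, which defeats the purpose of the retest. In both cases a visit missed after Month 12 changes the Month 12 outcome.

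**Working it through.** There is no published figure to reproduce, so the check applies the written rules to a worked record.

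**Inputs from the SAP:** the boundary rule (13.5.1), Table 8, phase before window (13.2.1), the Month 12 window (Table 2), and Appendix 8 steps 3.1 to 3.2.1.

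**Input from the schedule of activities:** viral load is drawn at Months 1, 2, 4, 8 and 12. Footnote b makes Dose 8 (Month 14) follow the Dose 6 pattern, which has no viral load, and Dose 9 (Month 16) follow the Dose 7 pattern, which has one.

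**Illustrative dates (assumed):** oral lead-in starts 5 Jan 2021 and the first injection is on 5 Feb 2021. The targets are then 5 Jan 2022 (Month 12), 5 Mar 2022 (Month 14) and 5 May 2022 (Month 16). The participant is on treatment throughout.

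- Month 12 study day = (5 Jan 2022 − 5 Jan 2021) + 1 = 366.
- Snapshot window = 366 − 42 to 366 + 42 = days 324 to 408.
- The nearest other scheduled viral loads are Month 8 (122 days earlier) and Month 16 (120 days later). Both lie outside the window, so neither can replace the Month 12 value.

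| Case | Boundary date | Month 12 sample or retest | Snapshot result |
|---|---|---|---|
| a. Month 14 attended | 5 Mar 2022 | Sample in Intervention | <50 |
| b. Month 14 missed, last contact = Month 12 visit | 5 Jan 2022 | Sample in Extension | No virologic data (on study, missing in window) |
| c. Month 14 missed, last contact one day after Month 12 | 6 Jan 2022 | Sample in Intervention | <50 |
| d. Month 12 value 60 c/mL, suppressed retest 21 days later is the last contact | 26 Jan 2022 | Sample in Intervention, retest in Extension | ≥50 |
| e. As d, but Month 14 attended | 5 Mar 2022 | Both in Intervention | <50 |

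In case b the sample is windowed with Table 3, whose first row is Month 14. As printed, that row runs from the nominal Month 14 day (366) to 425 − floor[(486 − 425)/2] = 395, so the Month 12 sample is labelled Month 14. Table 3 has no Month 12 row.

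**Size per participant:** 1/450 = 0.22 percentage points, so 5 participants = 1.11 and 10 = 2.22. The 450 is the planned number of evaluable participants (SAP 2.4.1). With the 474 planned enrolled, 1/474 = 0.21.

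**Check of the fix:** target dates fall on the same day of the month, capped at the 28th, so Month 14 is two calendar months (59 to 62 days) after Month 12. The Month 12 window ends at +42 days, which leaves at least 59 − 42 = 17 days. With the boundary at the projected Month 14 target (day 425), the Month 12 sample (day 366) and the retest (day 387) both stay in the Intervention Phase, and cases b and d return <50.

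**Conflict on Extension entry:** SAP 13.3.1 says a participant enters the Extension Phase by having a Month 14 visit, and Table 6 uses that visit date. SAP 13.5.1 provides for people who continued without one. Table 9 and the footnote to shell DISP_T1 accept an assessment at any Extension nominal visit.

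**The case against.** The strongest reply is that the Intervention Phase condition is not absolute. SAP 13.5.3 says typically, cites Table 3 alongside Table 2, and defers to Appendix 8, whose steps ask only for an on-treatment viral load during Month 12. SAP 7.1.3 names no phase either. On those texts alone the sample would count. This stands as far as it shows that sections disagree. It does not remove the problem, because 13.2.1 assigns phase first and Extension samples then meet a table with no Month 12 row.

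A literal reading of 13.3.1 would also keep these participants in the Intervention Phase. That is one side of an internal conflict, and 13.5.1 is the specific rule for this case.

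The trigger is narrow, and this stands. Protocol 7.3 requires an attempt to contact anyone who misses a visit, and a single recorded contact after the Month 12 sample rescues it (case c). An attempt is not necessarily a contact, however, and the SAP does not define last contact date for this rule. Snapshot is a Month 12 deliverable and the end-of-study versions use observed cases, so only people with a Month 16 or later visit before the Month 12 data cut are exposed. Such people can exist, because SAP 3.2 holds the analysis until everyone has finished Month 12.

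A reader might go further and infer that adverse events and medications of people without a Month 14 injection belong to no phase. Tables 7 and 10 end the Intervention Phase at the Month 14 visit but start the Extension Phase at the injection, for example "Date of Nominal Month 14 Injection ≤ Date ≤ Safety Follow-up visit date". The documents do not establish that loss. SAP 13.5.1 makes the visit date equal the injection date where one was given and supplies fallbacks where it was not. The missing-date rule in Table 7 itself uses the injection label for the end of the Intervention Phase. Two labels for one derived date is the likelier explanation.

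**Conclusion.** Wrong as written, with a small expected effect. Followed in the order the SAP sets, the rules can turn a measured Month 12 result into missing data, or discard a suppressed retest and leave the first value standing.

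A participant is affected only if all of these hold: Month 14 was missed; a Month 16 or later visit took place before the Month 12 data cut; and no contact was recorded after the Month 12 sample (or, in the retest case, after the retest). The conclusion also assumes that the programmer follows 13.5.1, 13.2.1 and 13.5.3 where they conflict with 13.3.1 or with the silence of Appendix 8 on phase.

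It is tempting to turn this into a bias of a percentage point or more. The documents give no rate of missed Month 14 visits and no number continuing into the Extension Phase, so no total can be supported. What can be said is about 0.22 points per affected participant, on a secondary, descriptive endpoint.

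**What to change.** 1. In SAP 13.5.1, replace the fallback for a missed Month 14 visit with the projected Month 14 target date. Every value eligible for the Month 12 Snapshot then stays in the Intervention Phase. A Month 12 visit delayed past the projected Month 14 date would already be outside the ±42-day window.
2. In SAP 13.3.1, align the Extension entry rule and Table 6 with 13.5.1, Table 9 and the DISP_T1 footnote, so that an assessment at any Extension nominal visit is enough.
3. As a consistency correction, use the nominal Month 14 visit date instead of the injection date in Tables 7 and 10 and in the missing-date rule, so that the Intervention Phase ends and the Extension Phase starts on the same date.

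The cost is SAP wording and one derivation line. No data collection changes.
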